10.3.9. Phase 3 Table of Assessments

Concept	Assessment	Visit
Participant eligibility measures	Screening survey	Time 1
	Opioid Use Disorder diagnosis based on the DSM-5 checklist (American Psychiatric Association, 2013)	Time 1
	Timeline Follow-Back interview (Sobell et al., 1988) to assess opioid and other substance use in past 30 days	Time 1
	Current suicidality based on 3 items from the Concise Health Risk Tracking—Self Report (CHRT-SR) Suicidal Behavior Evaluation (Trivedi et al., 2011)	Time 1
	Urine drug screen [REDACTED] [REDACTED] [REDACTED] [REDACTED] (https://cliawaived.com/fentanyl-rapid-tests-20.html)	Time 1
Baseline sociodemographics	Baseline survey using PhenX Toolkit items (Hamilton et al., 2011)	Time 1
User experience measures	Social Media Usability scale (Lund, 2001) and open-ended questions	Time 2
Opioid use outcome measures	Urine drug screen [REDACTED] [REDACTED] [REDACTED] [REDACTED]	Time 2

	(https://cliawaived.com/fentanyl-rapid-tests-20.html)	
	Timeline Follow-Back interview (Sobell et al., 1988) to assess opioid and other substance use in past 30 days or since study enrollment	Time 2
MOUD retention	Timeline Follow-Back interview (Sobell et al., 1988) MOUD use in past 30 days or since study enrollment	Time 2
Psychiatric symptom measure	K6 scale (Kessler et al., 2002)	Time 1, Time 2
Spirituality measure	Items from World Health Organization's Quality of Life Spirituality, Religion, and Personal Beliefs measure (WHOQOL SRPB Group, 2006)	Time 1, Time 2

10.3.10. Data Collected by Study Staff

Recruitment feasibility measures documented by study staff include the number of potential participants screened, number eligible, and number enrolled out of those eligible. Study retention will be defined as the proportion completing the end of intervention Follow-up Survey and a UDS.

For intervention engagement assessment, study staff will extract data weekly from the Facebook application programming interface (Facebook, 2020) using an extraction program based on a Python module (<https://pypi.org/project/facebook-scrapers/>) which we have utilized in prior work (Sinicrope et al., 2022). Standard engagement metrics for social media health promotion interventions (Pagato et al, 2016) include Facebook analytics of the number of posts 'seen by' group members, reactions (e.g., likes, loves), and comments. Engagement *by participant* includes the number of comments, reactions, responses to a Facebook poll or other activities, attendance at live events (e.g., guest speakers) and posts initiated (i.e., participant created a post with text, image, and/or video). A total engagement count will be calculated from these metrics. The text of participant-generated posts and comments will be exported into an excel spreadsheet for analysis of content. Unlike many web-based platforms, Facebook analytics do not provide time spent on the Facebook page.

10.3.11. End of Intervention Form

This form tracks the participant's status with regard to the intervention in Phase 3. It will be completed by a member of the study staff at the follow-up visit (for participants who complete study participation).

10.3.12. Study Completion Form

This form tracks the participant's status in the study. It will be completed by a member of the study staff at the follow-up visit or after the six-week visit window lapses for participants who do not complete this final follow-up. This form is used in data analyses to address variables such as treatment retention and completion. This form also provides a location for the site LI attestation of review of all study data.

DRAFT

11. CLINICAL AND SAFETY ASSESSMENTS

11.1. Adverse Events (AEs) and Serious Adverse Events (SAEs)

In Phases 1 and 3, AEs and SAEs may be spontaneously reported to study staff at any visit following consent. AEs and SAEs suggesting medical or psychiatric deterioration will be brought to the attention of a study clinician for further evaluation and management. AE and SAE reporting is according to the reporting definitions and procedures outlined in the protocol and in accordance with applicable regulatory requirements. For purposes of this study, the following AEs do not require reporting in the data system but is captured in the source documentation as medically indicated:

Grade 1 (mild) unrelated adverse events: This would typically include mild physical events such as headache, cold, etc., that were considered not reasonably associated with the use of the intervention.

In Phase 3, study staff will assess during the follow-up visit by asking the participant if they visited the Emergency Department (ED), were hospitalized, or had an overdose since enrollment and to briefly describe the event. The study staff will inform the participant that they should contact the study staff immediately if they have an ED visit, are hospitalized, or have an overdose at any point in the study after consent.

For AEs and SAEs, we considered obtaining objective information (e.g., on hospitalizations, ER visits, overdoses) but decided this would not be feasible for this treatment development study. We are recruiting women from the local community and will rely on staff referrals from (1) multiple addiction treatment programs, (2) community clinics and programs throughout the Metropolitan area, and (3) friends or colleagues affiliated with the CAC. We are not recruiting women at specific addictions treatment programs, or from Mayo Clinic, Hennepin Healthcare, or another health system, where medical record release forms and data-sharing agreements could be readily obtained with the permission of participants. However, through this preparatory project, we are building important relationships with community clinic providers and staff who will refer patients to the study and thus building the foundation for the next step in this research where we could work with specific clinics to provide such information. In this study, we will account for AEs using self-report as well as documenting any spontaneous reports from secondary contacts in the event we are not able to reach a participant for the follow-up visit. The risk of adverse events associated with the intervention is minimal because women are required to be currently using MOUD.

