In our moderated Facebook intervention, it is impossible to know in advance what might be posted by users, and it is possible that misinformation or postings that might cause emotional discomfort could occur. Participants will be encouraged to contact the study coordinator if any issue arises that causes them to feel uncomfortable. There are also some minimal risks with respect to confidentiality. As a member of a secret Facebook group, participants will be asked to discuss their own opioid recovery journeys and participate in discussions about moderated postings regarding AIAN opioid use, readiness to maintain their recovery from opioids, and opioid treatment resources, among others. Thus, it is possible that health information or other personal information about study participants or other AIAN members could be disclosed on Facebook postings. To ameliorate concerns, a list of do's and don'ts for posting on the secret Facebook page will be posted at the front of the page so that whenever a participant joins the Facebook group, they will be reminded of these guidelines for sharing information, protecting confidentiality, and posting appropriately. Participants will be asked or encouraged to not mention specific names of people in their house or community. A trained moderator will monitor user postings and guide participants through culturally appropriate postings that do not violate confidentiality or harm intervention group members. If someone is offended by the postings,

they can message the moderator to resolve any concerns. Any adverse events related to the Facebook group will also be handled by the DSMP, if necessary. Despite these precautions, we do not anticipate any adverse consequences of participating in the intervention. In the beta-testing of a Facebook intervention for nicotine use among AIAN people (Sinicrope et al., 2022), one participant shared content outside the group on a personal Facebook page. When this occurred, the moderator sent the participant a private message, redirecting the participant to the group rules. There were no other group confidentiality or boundary violation incidents. We will remind participants in the consent form and a script in the content library to not share personal information with potential guest speakers in order to prevent confidentiality breaches.

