17.3.4 Safety Analysis

Descriptive statistics (frequencies and percentages) will be used to summarize AEs and SAEs. AEs, including SAEs, will be summarized by body system and preferred term using MedDRA codes (per The Medical Dictionary for Regulatory Activities). AEs will be presented as: (1) the number and proportion of participants experiencing at least one incidence of each event overall; and (2) the total number of each event overall in tabular form.

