18.19.1 Adverse Events (AEs)

Standard definitions for adverse events and serious adverse events, their identification, characterization regarding severity and relationship to therapy and processing are described in Appendix A.

For the purpose of this study, the following AEs will not require reporting in the data system but will be captured in the source documentation as medically indicated:

Grade 1 (mild) unrelated adverse events: This would typically include mild physical events such as headache, cold, etc., that were considered not reasonably associated with the use of the intervention.

Reportable AEs will include self-reported trips to the Emergency Department or clinical deterioration (based on the K6 scale score) indicated on the end-of-intervention follow-up survey. The study staff will follow up with the participant to determine if the AE was related to the

intervention. Participants will be asked to report any reportable AEs to the study staff if they occur during their active participation.

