2.0 OVERSIGHT OF CLINICAL RESPONSIBILITIES

A. Site Lead Investigator

The site's LI (LI) is responsible for study oversight, including ensuring human research subject protection by designating appropriately qualified, trained research staff and medical clinicians to assess, report, and monitor adverse events.

All adverse events (AEs) occurring during the course of the study will be collected, documented, and reported by the investigator or sub-investigators according to the Protocol.

The occurrence of AEs and serious adverse events (SAEs) will be assessed in the follow-up survey via self-report questions on trips to the Emergency Department, hospitalizations, and overdoses. Serious adverse events will be followed until considered resolved or stable.

B. Safety Reporting

The LI (LI) may appoint a Site Medical Clinician (MD, DO, NP, or PA) or utilize the Mayo Clinic on-call physician for this study, who will review or provide consultation for each Adverse Event (AE) and Serious Adverse Event (SAE) as needed. These reviews will include an assessment of the possible relatedness of the event to the study intervention or other study procedures. The Site Medical Clinician will also provide advice for decisions to exclude, refer, or withdraw participants as required. A site clinical psychologist or psychiatrist may also review AEs and SAEs as needed. The study staff will determine which safety events require expedited reporting to NIDA and regulatory authorities. This will include events that are serious, related, and unexpected. The study staff will be trained to monitor for and report AEs and SAEs, and participants will report AEs and SAEs at the follow-up visit.

The study site has established practices for managing medical and psychiatric emergencies, and the study staff will continue to utilize these procedures. Treatment providers at the site will be responsible for monitoring participants for possible clinical deterioration or other problems, and for implementing appropriate courses of action.

Voluntary Regulatory Reporting in non-IND Trials:

For non-IND trials, if an event meets expedited reporting criteria (serious, related and unexpected) the Safety Monitor/Medical Monitor or designee will voluntarily report to FDA/Regulatory Authorities using the MedWatch Form 3500 or similar.

C. Data and Safety Monitoring

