drugs. Facebook posts and comments may cause emotional discomfort for the participants depending on what other members and moderators post. There is a chance that the participants experience withdrawal symptoms as they continue to abstain from opioids, but this risk is minimal because they would have already abstained from illicit opioid use for at least 30 days at screening. What symptoms may occur are expected to be mild and may consist of nausea, abdominal discomfort, muscle and joint pain, perspiration, runny nose and eyes, yawning, irritability, and anxiety. Since this FB intervention is not anonymous, confidentiality of health information could be compromised. However, the intervention group moderators will emphasize that all information shared in the group should stay in the group, and any samples and identifiers outside of the intervention will be destroyed.

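### No described item asks about distress caused by group postings or about confidentiality breaches, both named as risks, and a breach without medical consequence has no planned count

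*Combined protocol and SAP*

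**What the plan says.** **Risks named for the group.** Section 4.3.1 accepts that "it is possible that misinformation or postings that might cause emotional discomfort could occur". It treats disclosure of personal or health information as a further risk. It also reports that, in an earlier beta-test of a Facebook group for nicotine use, "one participant shared content outside the group on a personal Facebook page". Appendix B (2.0, Study Specific Risks) repeats that "Facebook posts and comments may cause emotional discomfort for the participants depending on what other members and moderators post", and adds that confidentiality could be lost because the group is not anonymous.

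**What is asked.** Section 11.1 has staff assess events at follow-up "by asking the participant if they visited the Emergency Department (ED), were hospitalized, or had an overdose since enrollment". Section 10.3.8 lists the same three events, and Appendix B (2.0, A) says the follow-up survey will assess AEs and SAEs "via self-report questions on trips to the Emergency Department, hospitalizations, and overdoses".

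**What else is collected.** The K6 is given at baseline and follow-up (10.3.8, 11.2). Section 18.19.1 makes deterioration on the K6 a reportable AE, and staff then establish whether it was related to the intervention. Appendix B (2.0, C) has staff and moderators look for AEs at each scheduled contact, including online contact.

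**What is tabulated.** Under 17.3.4, "AEs, including SAEs, will be summarized by body system and preferred term using MedDRA codes". Appendix A limits an AE to an untoward medical occurrence.

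**The concern.** The risk section and the safety collection do not line up. The three structured questions suit a general medical safety screen. The two harms particular to a private Facebook group, being upset by what is posted and having one's disclosure or membership leak, have no dedicated question. The second also has no place in the safety table unless it leads to something medical.

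The secondary objective is feasibility and acceptability (5.2), and the results are meant to support a pilot RCT (6.1). For women disclosing opioid recovery in a group, whether postings caused distress and whether privacy held are among the most useful things a beta-test can report. As planned, that report would rest on what participants volunteer and what moderators remember.

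**Working it through.** The plan gives no figure to reproduce. The check is whether each named harm has a question and a count, followed by some arithmetic on size.

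**1. Tracing each harm through the plan**

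| Step | Distress from postings | Confidentiality breach |
|---|---|---|
| Named as a risk | Yes (4.3.1; Appendix B) | Yes (4.3.1; Appendix B) |
| One of the three structured events (10.3.8, 11.1, Appendix B) | No | No |
| Other structured measure | K6, which is general and does not ask about cause | None described |
| Meets the AE definition (Appendix A) | If it amounts to a medical occurrence | Not by itself |
| Can enter the 17.3.4 table | Yes, if recorded as an AE | Not without a medical consequence |
| Other routes | Spontaneous report, open-ended answers | IRB report as an unanticipated problem (18.2), open-ended answers (17.3.1.2) |
| Planned count specific to this harm | None | None |

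**2. How far the K6 covers distress.** Section 11.2 describes it as measuring nonspecific distress over the past month. No numeric threshold is given for deterioration (18.19.1) or for the increase that prompts follow-up (11.2), and 17.3 plans no summary of K6 change. Timing also matters. Take recall as 30 days and the group as 30 days, and assume that the six-week window in 10.3.8 runs from the group's end. The overlap for a visit d days after the end is max(0, 30 − d):

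| d (days) | 0 | 14 | 28 | 30 | 42 |
|---|---|---|---|---|---|
| Days of the group covered | 30 | 16 | 2 | 0 | 0 |

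A prompt visit covers the whole group period. A visit between day 30 and day 42 is still inside the window and covers none of it.

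**3. Is a breach realistic at this sample size?** Section 4.2 gives n = 10 for the earlier beta-test and 4.3.1 gives one incident: 1/10 = 10%, exact (Clopper-Pearson) 95% interval 0.25% to 44.5%. For an assumed rate p per woman, and treating the 10 women as independent, P(at least one) = 1 − (1 − p)^10:

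| p | 5% | 10% | 20% | 30% |
|---|---|---|---|---|
| P(at least one in 10) | 40.1% | 65.1% | 89.3% | 97.2% |

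Women in one group see the same postings, so independence is only an approximation.

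**4. What a zero would mean if the items were asked.** With 0 of 10, the upper limit is 1 − 0.05^(1/10) = 25.9% (one-sided 95%) or 1 − 0.025^(1/10) = 30.8% (two-sided 95%). Without the question, no such limit can be attached, because there is no defined set of women who answered.

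**The case against.** The strongest reply is that distress is far from ignored. The K6 is given specifically to look for symptom change while women are in the group, its deterioration is a reportable AE, and relatedness is followed up. Staff and moderators evaluate AEs at each contact, AEs go on a form for each participant (19.3), and they are summarized monthly (17.3.5). Only mild events that are unrelated to the intervention are exempt from the data system (11.1), so mild distress related to the group that qualifies as an AE is not exempt. All of this stands. A reader might infer that the plan asks about nothing beyond three medical events, or that distress is never asked about or tabulated. The documents contradict both.

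The second reply is that incidents can surface elsewhere. Open-ended answers and group text are content-analysed (17.3.1.2), moderator-participant discussions are reviewed weekly (19.9), moderators take incidents to a consultant (10.2.3), unanticipated problems go to the IRB, and participant noncompliance can be recorded as a protocol deviation (18.18). These routes are real, but each depends on someone volunteering or classifying the event, and none leads to a planned count of breaches. Moderators may remove posts at their checks every 1-2 days (10.3.5) while data are extracted weekly (10.3.10), so a removed post may never reach the content analysis.

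Third, a reader might take the earlier incident to mean that 1 of 10 then would become 0 of 10 breaches detected now. The documents do not support that. The earlier team noticed its incident, and no survey item is described as having been needed. Section 4.3.1 also does not say that anyone's private information was exposed. The incident shows only that such an event would be missing from the AE table.

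Finally, this is a descriptive beta-test of 10 women in which safety is not a listed outcome, and no section plans a claim of no intervention-related harm. That limits the weight of the point but does not remove it. The Follow-up Survey and moderator guidelines themselves are not in the text, so the point concerns the items the protocol describes.

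**Conclusion.** The point holds in a limited form, as an inexpensive improvement. General distress is captured, though by a measure that does not ask about cause and that may miss the group period if the visit is late. No described item asks about distress caused by postings or about confidentiality breaches. A breach with no medical consequence has no planned count and falls outside the only safety table.

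The size is modest and uncertain. One incident in 10 earlier participants is compatible with rates from 0.25% to 44.5%. At an assumed 10%, the chance of at least one event among 10 women is 65%. The conclusion assumes that the unseen Follow-up Survey contains no such items beyond those described. If it does, only the missing count in 17.3.4 remains. The K6 timing result further assumes that the window starts when the group ends.

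**What to change.** 1. **Follow-up Survey (10.3.8).** Add two yes/no items with free text: whether anything in the group distressed her, and whether anything she shared, or the fact of her membership, went outside the group.
2. **Moderator log.** Have the existing moderators record each removed post, private redirect, and confidentiality or boundary incident, by study ID and date.
3. **Section 17.3.4.** Add one descriptive table, outside MedDRA, giving the number of women and the number of incidents. For the survey items, the denominator is the women who answered. Keep survey reports and logged incidents on separate rows: the survey counts women affected, while the log may identify the woman whose post or action prompted the entry.

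Sample size, eligibility and the intervention are unchanged. The cost is a few minutes of participant and moderator time, one extra table, and notification to the IRB. The reported harm count may also look less favourable than it otherwise would.

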11.2. K6 Scale

In Phase 3, we will use the K6 scale (Kessler et al., 2002) at baseline and follow-up assessments. Included in the PhenX toolkit (Hamilton et al., 2011), the K6 is a screening measure that assesses psychological distress including depressive and anxiety symptoms over the past month. The K6 measures distress with six questions (e.g., “How often did you feel nervous?” “How often did you feel hopeless?”) scored on a five-point Likert scale ranging from 0=none of the time to 4=all of the time. Total scores can range from 0 to 24. The K6 scale is a widely used indicator of nonspecific psychological distress and is highly correlated with mental illness. Moreover, studies have shown that having a score of 13 or greater on the K6 is a strong indicator of the presence of a DSM

diagnosable psychiatric disorder with considerable disability (Furukawa et al., 2003; Kessler et al., 2003). The K6 has been validated in general population samples (Forman-Hoffman et al., 2014) and among AIAN adults specifically (Mitchell & Beans, 2011).

If a K6 score of ≥ 13 is prevalent at baseline or follow-up, or if a substantial increase in scores from baseline is noted at follow-up, the LI or one of the study clinicians will follow-up with the participant for further assessment and initiate referral for additional mental health assessment and care as described in the DSMP.

